### 8.3.2. Regression Modeling

Logistic and multivariable linear regression will be utilized to test for the effects of prior vaccination with 2013 A/H7N9 IIV and the addition of AS03 adjuvant to 2017 A/H7N9 IIV on seroconversion and GMT at 21 days post vaccination, respectively, for the PP population. Similar models will be fit for both HAI and Neut antibody results.

Logistic regression will be fit to examine the relationship of HAI seroconversion at 21 days post vaccination with study group, stratum, and the interaction of study group and stratum. If the available titer data meets the required assumptions of normality after log transformation, multiple linear regression will be fit to examine the relationship of log transformed titers at 21 days post vaccination with study group, stratum, and the interaction of study group and stratum. Both models will be fit with and without adjustment for the following covariates (*Z*): sex (female, male), age (19-35 years, 35-50 years, 51-70 years), BMI (<30, ≥30), and prior receipt of seasonal influenza vaccine (none in past 2 seasons, at least one in past 2 seasons). Modeling assumptions will be checked using standard diagnostic methods (e.g., using the INFLUENCE option in PROC LOGISTIC or PROC GLM). Parameter estimates and odds ratio estimates for the logistic models will be presented in [Table 36](#), [Table 37](#), [Table 38](#), and [Table 39](#). Parameter estimates for the multiple linear regression models will be presented in [Table 40](#), [Table 41](#), [Table 42](#), and [Table 43](#).

Model 1A: Logistic Regression (without covariate adjustment):

$$\text{logit}[P(\text{seroconversion})] = \beta_0 + \beta_1 \times \text{Study Group} + \beta_2 \times \text{Stratum} + \beta_3 \times \text{Study Group} * \text{Stratum}$$

Model 1B: Logistic Regression (with covariate adjustment):

$$\text{logit}[P(\text{seroconversion})] = \beta_0 + \beta_1 \times \text{Study Group} + \beta_2 \times \text{Stratum} + \beta_3 \times \text{Study Group} * \text{Stratum} + \beta_4 \times Z$$

Model 2A: Multiple Linear Regression (without covariate adjustment):

$$\log(\text{titer}) = \beta_0 + \beta_1 \times \text{Study Group} + \beta_2 \times \text{Stratum} + \beta_3 \times \text{Study Group} * \text{Stratum} + \varepsilon$$

Model 2B: Multiple Linear Regression (with covariate adjustment):

$$\log(\text{titer}) = \beta_0 + \beta_1 \times \text{Study Group} + \beta_2 \times \text{Stratum} + \beta_3 \times \text{Study Group} * \text{Stratum} + \beta_4 \times Z + \varepsilon$$

Subjects missing data for one or more covariates will be excluded from Models 1B and 2B.

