### 4.4.3. Method of Assigning Subjects to Treatment Groups (Randomization)

Enrollment/randomization will be performed through the enrollment module in the electronic data capture system maintained by the Statistical and Data Coordinating Center (SDCC).

Eligible subjects will be stratified by prior receipt of 2013 A/H7N9 IIV with or without adjuvants, clinical site, and prior receipt of licensed, seasonal influenza vaccine then randomly assigned with allocation (1:1) to one of two treatment arms to receive 1 dose of 2017 A/H7N9 IIV at 3.75 mcg HA per dose with or without AS03 adjuvant. There is a total of ten strata with maximum enrollments outlined in [Table 1](#).

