### 4.4.5. Selection and Timing of Dose for Each Subject

Each subject is to be randomly assigned to a study group which will define the receipt of adjuvant for the study vaccination administered on Day 1. Study groups are defined by a combination of prior receipt of 2013 A/H7N9 IIV and study product randomization as shown in [Table 1](#).

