
Note: N = Number of subjects in the per-protocol population in the given stratum; N* = Number of subjects in the per-protocol population in the given stratum and study group; n = number of subjects with available result; GMT = Geometric Mean Titer; GMFR = Geometric Mean Fold Rise.
 
a Confidence Interval calculated based on the student's T distribution.
 
b Exact binomial confidence interval calculated using the Clopper-Pearson methodology.
										

Tables with similar format:

**Table 35: Summary of Neutralizing Antibody Against A/Hong Kong/125/2017 (H7N9) by Stratum, Study Group and Prior Seasonal Influenza Vaccination at 21 Days Post Vaccination, Per-Protocol Population**

**Table 36: Logistic Regression Model to Evaluate the Relationship of AS03 Adjuvant and Stratum with HAI Seroconversion Against A/Hong Kong/125/2017 (H7N9) at 21 Days Post Study Vaccination, Per Protocol Population**

Model Parameter	Parameter Levels	Parameter Estimate	SE	p-value	Odds Ratio	95%CI
Intercept	-	xxx.x	xxx.x	x.xxx	-	-
Study Group	3.75 mcg A/H7N9 (reference)	-	-	-	-	-
	3.75 mcg A/H7N9 + AS03	xxx.x	xxx.x	x.xxx	xx.x	xx.x-xx.x
Stratum	A/H7 IIV-Naïve (reference)	-	-	-	-	-
	2013 A/H7N9 IIV 15 mcg or 45 mcg unadjuvanted	xxx.x	xxx.x	x.xxx	xx.x	xx.x-xx.x
	2013 A/H7N9 IIV with MF59/AS03 then 2013 A/H7N9 IIV 15 mcg	xxx.x	xxx.x	x.xxx	xx.x	xx.x-xx.x
	2013 A/H7N9 IIV + MF59	xxx.x	xxx.x	x.xxx	xx.x	xx.x-xx.x
	2013 A/H7N9 IIV + AS03	xxx.x	xxx.x	x.xxx	xx.x	xx.x-xx.x
Study Group * Stratum	A/H7 IIV-Naïve * 3.75 mcg A/H7N9 + AS03	-	-	-	-	-
	2013 A/H7N9 IIV 15 mcg or 45 mcg unadjuvanted * 3.75 mcg A/H7N9 + AS03	xxx.x	xxx.x	x.xxx	xx.x	xx.x-xx.x
	2013 A/H7N9 IIV with MF59/AS03 then 2013 A/H7N9 IIV 15 mcg * 3.75 mcg A/H7N9 + AS03	xxx.x	xxx.x	x.xxx	xx.x	xx.x-xx.x
	2013 A/H7N9 IIV + MF59 * 3.75 mcg A/H7N9 + AS03	xxx.x	xxx.x	x.xxx	xx.x	xx.x-xx.x
	2013 A/H7N9 IIV + AS03 * 3.75 mcg A/H7N9 + AS03	xxx.x	xxx.x	x.xxx	xx.x	xx.x-xx.x

Note: N = XX subjects with results available at 21 days post vaccination in the per protocol population. XX subjects missing covariate data were excluded from this analysis.

P-values will be generated for study group, stratum, and the study group by stratum interaction using a likelihood-ratio test.

The p-value for the study group term was 0.xxx; The p-value for the stratum term was 0.xxx; The p-value for the study group by stratum interaction term was 0.xxx.

Tables with similar format:

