**Table 39: Logistic Regression Model to Evaluate the Relationship of AS03 Adjuvant and Stratum with Neut Seroconversion Against A/Hong Kong/125/2017 (H7N9) at 21 Days Post Study Vaccination, Adjusted for Baseline Covariates, Per Protocol Population**

**Table 40: Multiple Linear Regression Model to Evaluate the Relationship of AS03 Adjuvant and Stratum with Log-Adjusted HAI Titer Against A/Hong Kong/125/2017 (H7N9) at 21 Days Post Study Vaccination, Per Protocol Population**

Model Parameter	Parameter Levels	Parameter Estimate	SE	95% CI	p-value
Intercept	-	xxx.x	xxx.x	-	x.xxx
Study Group	3.75 mcg A/H7N9 (reference)	-	-	-	-
	3.75 mcg A/H7N9 + AS03	xxx.x	xxx.x	xx.x-xx.x	x.xxx
Stratum	A/H7 IIV-Naive (reference)	-	-	-	-
	2013 A/H7N9 IIV 15 mcg or 45 mcg unadjuvanted	xxx.x	xxx.x	xx.x-xx.x	x.xxx
	2013 A/H7N9 IIV with MF59/AS03 then 2013 A/H7N9 IIV 15 mcg	xxx.x	xxx.x	xx.x-xx.x	x.xxx
	2013 A/H7N9 IIV + MF59	xxx.x	xxx.x	xx.x-xx.x	x.xxx
	2013 A/H7N9 IIV + AS03	xxx.x	xxx.x	xx.x-xx.x	x.xxx
Interaction: Study Group*Stratum	A/H7 IIV-Naive * 3.75 mcg A/H7N9 + AS03	-	-	-	-
	2013 A/H7N9 IIV 15 mcg or 45 mcg unadjuvanted * 3.75 mcg A/H7N9 + AS03	xxx.x	xxx.x	xx.x-xx.x	x.xxx
	2013 A/H7N9 IIV with MF59/AS03 then 2013 A/H7N9 IIV 15 mcg * 3.75 mcg A/H7N9 + AS03	xxx.x	xxx.x	xx.x-xx.x	x.xxx
	2013 A/H7N9 IIV + MF59 * 3.75 mcg A/H7N9 + AS03	xxx.x	xxx.x	xx.x-xx.x	x.xxx
	2013 A/H7N9 IIV + AS03 * 3.75 mcg A/H7N9 + AS03	xxx.x	xxx.x	xx.x-xx.x	x.xxx

Note: N = XX subjects with results available at 21 days post vaccination in the per-protocol population. XX subjects missing covariate data were excluded from this analysis.

Tables with similar format:

**Table 41: Multiple Linear Regression Model to Evaluate the Relationship of AS03 Adjuvant and Stratum with Log-Adjusted Neut Titer Against A/Hong Kong/125/2017 (H7N9) at 21 Days Post Study Vaccination, Per Protocol Population**

**Table 42: Multiple Linear Regression Model to Evaluate the Relationship of AS03 Adjuvant and Stratum with Log-Adjusted HAI Titer Against A/Hong Kong/125/2017 (H7N9) at 21 Days Post Study Vaccination, Adjusted for Baseline Covariates, Per-Protocol Population**

Model Parameter	Parameter Levels	Parameter Estimate	SE	95% CI	p-value
Intercept	-	xxx.x	xxx.x	-	x.xxx
Treatment	3.75 mcg A/H7N9 (reference)	-	-	-	-
	3.75 mcg A/H7N9 + AS03	xxx.x	xxx.x	xx.x-xx.x	x.xxx
Stratum	A/H7 IIV-Naive (reference)	-	-	-	-
	2013 A/H7N9 IIV 15 mcg or 45 mcg unadjuvanted	xxx.x	xxx.x	xx.x-xx.x	x.xxx

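### In SAP Tables 36–43 the only AS03 row is the effect in the naïve stratum; no table prints the AS03 effect with a confidence interval in a primed stratum, and there is no rule for an empty cell

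*SAP*

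**What the plan says.** SAP 8.3.2 states that the models are meant "to test for the effects of prior vaccination with 2013 A/H7N9 IIV and the addition of AS03 adjuvant to 2017 A/H7N9 IIV", on Day 21 seroconversion (logistic) and titer (linear), in the per-protocol population. The logistic model relates "HAI seroconversion at 21 days post vaccination with study group, stratum, and the interaction of study group and stratum"; the Neut and linear models use the same terms. They are fitted without covariates (Models 1A, 2A) and with them (1B, 2B). The section's text names no reference levels and no contrasts. For the linear models it says "Parameter estimates for the multiple linear regression models will be presented in" Tables 40–43, which have columns for estimate, SE, 95% CI and p-value but none for a GMT ratio.

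The shells for Tables 36, 38, 40 and 42 mark unadjuvanted 3.75 mcg and the A/H7-naïve stratum as reference and put dashes in the naïve-by-AS03 interaction row. The other four tables have similar format. Each primed stratum then has an interaction row, such as "2013 A/H7N9 IIV + MF59 * 3.75 mcg A/H7N9 + AS03", and in the logistic tables that row fills the Odds Ratio column. A footnote to Table 36 adds likelihood-ratio p-values for the three terms.

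Terms vary elsewhere. SAP 4.4.5 says "Study groups are defined by a combination of prior receipt of 2013 A/H7N9 IIV and study product randomization", which makes ten groups, and SAP 4.4.3 says "There is a total of ten strata with maximum enrollments outlined in" Table 1. The model shells use two arms and five strata.

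For model checking, 8.3.2 offers standard diagnostics only. It gives no method for a cell in which nobody, or everybody, seroconverts.

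**The concern.** Protocol 2.2 names the adjuvant effect in primed people as something to assess. Protocol 3.2.3 lists, as an exploratory outcome, the relation of adjuvant use in prime and/or boost to H7 antibody. The model tables are the planned output closest to that question, and the only one with covariate adjustment. Yet the row that looks like the AS03 effect concerns unprimed subjects only, and the rows that look like AS03 effects in primed strata are comparisons with the naïve effect. A reader of Tables 36–39 could take either for the adjuvant effect in primed subjects.

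The reference cell is also a fragile choice. Group 10 gets one unadjuvanted 3.75 mcg dose with no priming, and every logistic stratum row, as well as the AS03 row, is measured against it.

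**Working it through.** **Inputs.** Planned cell sizes come from Table 1 of both documents: 30 per arm in the naïve and adjuvanted-then-15 mcg strata, and 50 per arm in the other three. Total 2 × (50 + 50 + 50 + 30 + 30) = 420; naïve 30 + 30 = 60; primed 360. The documents give no responder counts, so all counts below are assumed.

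**What each row estimates.** Let L(s,t) be the log odds in stratum s and arm t, with 0 = naïve or no AS03.
- AS03 row: L(0,1) − L(0,0), Group 9 v Group 10.
- Stratum row s: L(s,0) − L(0,0), priming without AS03.
- Interaction row s: [L(s,1) − L(s,0)] − [L(0,1) − L(0,0)], a log ratio of odds ratios.
- AS03 effect in primed stratum s: AS03 row + interaction row. This is not printed.

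**Illustration (Model 1A).**

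| Stratum | No AS03 v AS03 | AS03 odds ratio (95% CI), not printed |
|---|---|---|
| Unadjuvanted prime | 10/50 v 25/50 | (25×40)/(25×10) = 4.00 (1.65–9.72) |
| Adjuvanted then 15 mcg | 9/30 v 18/30 | (18×21)/(12×9) = 3.50 (1.20–10.2) |
| MF59 prime | 20/50 v 35/50 | (35×30)/(15×20) = 3.50 (1.53–8.01) |
| AS03 prime | 20/50 v 36/50 | (36×30)/(14×20) = 3.86 (1.67–8.91) |

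The printed AS03 row depends on the naïve cells alone:
- Naïve 3/30 v 4/30: (4×27)/(26×3) = 1.38 (0.28–6.80). The interaction rows print 2.89, 2.53, 2.53 and 2.79 (for example 4.00/1.385 = 2.89).
- Naïve 3/30 v 12/30: (12×27)/(18×3) = 6.00 (1.48–24.3). The interaction rows print 0.67, 0.58, 0.58 and 0.64.

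The primed effects are the same in both cases, yet the AS03 row lies below all of them in one and above all of them in the other.

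**Precision of the printed rows.** In the linear model, in SD units, the contrast within a 50 v 50 stratum has SE √(2/50) = 0.200. The interaction row for that stratum has √(2/30 + 2/50) = 0.327.

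**Can the interval be recovered?** Without covariates the within-stratum SE is √(SE²interaction − SE²AS03), exactly. In the first example SE²AS03 = 1/4 + 1/26 + 1/3 + 1/27 = 0.659, and for the unadjuvanted prime SE²interaction = 0.864, so the SE is √0.205 = 0.453. With covariates this is an approximation. In 1,000 simulated datasets with assumed covariate prevalences, its ratio to the true SE had a 95% range of 0.986–1.013 (linear) and 0.983–1.015 (logistic), with a worst case within 3.5%.

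**Empty cell.** The chance of no responders is (1 − p)ⁿ. Group 10 has n = 30, or about 29 after the assumed 3% exclusions.

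| True rate | n = 30 | n = 29 |
|---|---|---|
| 10% (lowest considered in Protocol 11.4.3) | 0.042 | 0.047 |
| 5% (assumed) | 0.215 | 0.226 |
| 2% (assumed) | 0.545 | 0.557 |

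L(0,0) enters the AS03 row, the four stratum rows and the four interaction rows, so all nine fail. A fit with Group 10 at 0/30 and Group 9 at 5/30 gave diverging estimates and SEs in the thousands on every one. The interaction likelihood-ratio statistic stayed finite (2.69, p = 0.61). Other empty or full cells cost less: Group 9 empty, five rows; a primed cell without AS03 empty, two; a primed AS03 cell at 100%, one.

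**The case against.** The strongest reply is that this is how any reference-coded interaction model reads, and that little is lost. Primed point estimates are the product of two printed odds ratios. Tables 22–27, which are topline, give each arm's results with intervals in every stratum, so unadjusted contrasts can be worked out. SAP 10 asks for three significant figures for coefficients, enough to rebuild the SEs. Table 36 adds global likelihood-ratio p-values. Protocol 11.6.3 makes the modelling optional, SAP 8.1 plans no formal hypothesis test, and no document requires a model-based AS03 contrast in each primed stratum. All of this stands, and it keeps the point minor. It does not supply a printed within-stratum effect, an exact covariate-adjusted interval or a correct label for the interaction rows; the likelihood-ratio tests give p-values, not estimates.

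A reader might infer from SAP 4.4.3 and 4.4.5 that study group has ten levels, so that the stratum and interaction terms are redundant. The documents do not support that as a fault in the model. SAP 8 speaks of stratum and group combinations, and the notes to Figures 2, 26, 32 and 35, like the model shells, set out two arms by five strata. It is an inconsistency of wording.

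A reader might also infer that an empty Group 10 is likely. At the lowest rate considered it is a 4–5% event; the higher figures rest on assumed rates. The single-arm exact intervals already cope with a zero cell descriptively.

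**Conclusion.** The point holds as a minor reporting and estimation gap. Followed as laid out, the plan prints a naïve-stratum effect (60 of 420) as its only AS03 row, heads four ratios of odds ratios as odds ratios, and directly prints no AS03 odds ratio or GMT ratio with interval for the 360 planned primed subjects. One empty reference cell would remove all nine AS03, stratum and interaction odds ratios from an assay's logistic tables.

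It would go too far to say that the primed AS03 effect cannot be obtained or that a primary result is at risk. An empty Group 10 leaves the within-stratum contrasts in primed subjects, the interaction likelihood-ratio test, the linear models and the by-arm tables unaffected. The reading of the rows rests on the shells' reference levels. The odds ratios in the illustration rest on assumed counts and show only that the AS03 row can miss the primed effects in either direction.

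**What to change.** 1. From Models 1A, 1B, 2A and 2B, report AS03 v no AS03 in each of the five strata, as an odds ratio or back-transformed GMT ratio with 95% CI (ESTIMATE or LSMEANS statements). Over eight tables that is 5 × 8 = 40 intervals, given as estimates without tests. Priming contrasts within each arm are optional.
2. Label the AS03 row 'naïve stratum', the stratum rows 'without AS03' and the interaction entries in the logistic tables 'ratio of odds ratios'. State the reference levels in 8.3.2, and align the use of study group and strata in 4.4.3, 4.4.5 and 8.3.2 with the two-arm by five-stratum layout.
3. Pre-specify that a logistic model with any stratum-by-arm cell at 0% or 100% is refitted with a sparse-data method, for example Firth penalised likelihood with profile-likelihood intervals.

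The cost is SAP wording, row labels and a few SAS statements; no new data are needed. The drawback of step 3 is slight shrinkage, only when triggered: with naïve 0/30 v 5/30 and the primed counts above, the Firth odds ratios in the primed strata are 3.86, 3.35, 3.41 and 3.75 against 4.00, 3.50, 3.50 and 3.86, about 3–4% lower.

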In general, clinical studies evaluating vaccines made from novel avian influenza viruses (e.g., A/H5N1, A/H7N7, 2013 A/H7N9) suggest that these vaccines are substantially less immunogenic than those from other novel subtypes (e.g., 2009 A/H1N1 pandemic virus), even when administered at high HA dosages [27, 28]. Due to the poor immunogenicity of A/H5 and A/H7 vaccines, the inclusion of adjuvants was evaluated to assess their ability to boost anti-viral serum IgG levels. In the US, aluminum salts are licensed as adjuvants in combination with several vaccines; however, their use in subvirion influenza A/H5N1 vaccines has shown either no effect or a very modest enhancement of immune responses compared to non-aluminum salt containing formulations [29-31]. In contrast, the use of oil-in-water emulsion adjuvants, most notably proprietary adjuvants AS03 and MF59 produced by GSK and Novartis (now Seqirus), respectively, has resulted in increased antibody responses to IIVs containing novel HAs in numerous clinical trials [32-36]. In an early study, dosage levels ranging from 3.75 to 30 mcg of A/H5N1 antigen administered with or without AS03 resulted in significant increases in antibody geometric mean titers (GMTs) in subjects who received the adjuvanted formulations [34]. These GMTs met the Committee for Medicinal Products for Human Use (CHMP) criterion for seroconversion rate (>40%) after a single dose with adjuvant. Following the second vaccine dose, all adjuvanted formulations complied with both CHMP and US Food and Drug Administration (FDA) criteria for seroconversion and seroprotection rates, whereas from the non-adjuvanted treatment arms only the 30 mcg formulation met the CHMP criterion for seroconversion [34]. GSK received approval for the registration of a pre-pandemic AS03-adjuvanted, monovalent inactivated influenza A/H5N1 virus vaccine by European regulatory authorities in 2008 and FDA approval of their Biologics License Applications (BLA) for an Influenza A (H5N1) Virus Monovalent Vaccine Adjuvanted (with AS03) in 2013.

Following the 2009 emergence of the novel A/H1N1 pandemic virus, the European Commission granted marketing authorization of GSK's egg-derived AS03-adjuvanted monovalent inactivated

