2.2 Scientific Rationale

As part of the US Government's past pandemic preparedness efforts, Sanofi Pasteur under contract to the Biomedical Advanced Research and Development Authority (BARDA)/DHHS, produced several novel pre-pandemic vaccines that were or are currently being evaluated by NIAID's VTEU sites to assess their safety, reactogenicity and immunogenicity when mixed prior to administration with either AS03 or MF59 oil-in-water adjuvants manufactured by GSK and Seqirus, respectively. In general, these "mix and match" clinical trials have demonstrated that adjuvant use results in a significant dose-sparing effect.

The large number of human infections starting with the "fifth wave" of outbreaks in late 2016 has increased the pandemic risk potential of influenza A/H7N9 viruses circulating in China. The Yangtze River Delta lineage, a distinct A/H7N9 viral lineage, has now emerged and has been associated with many of the fifth wave cases. Fifth wave A/H7N9 viruses have led to a broader geographic spread of infected birds and human cases within China than previously reported. Further, several influenza A/H7N9 viruses in the Yangtze River Delta lineage have recently acquired genetic changes characteristic of highly pathogenic avian influenza (HPAI) viruses and have now shown an increased ability to infect and kill poultry [56, 59]. To date, no cases of A/H7N9 from the new viral lineage have been identified in birds or people infected outside of China; however, a few cases have been identified in Hong Kong and Taiwan in infected travelers returning from China. Importantly, antigenic analysis of the fifth wave influenza A/H7N9 viruses and serological studies indicate that the stockpiled 2013 A/H7N9 IIV manufactured several years

ago does not induce protective HAI or Neut antibodies against the Yangtze River Delta lineage. Hence, there is broad consensus across DHHS and interagency leadership that a new vaccine should be developed that would be effective against the currently predominating influenza A/H7N9 viruses.

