
#### **4.5.2. Immunogenicity Variables**

Individual HAI and Neut results will be reported by the central immunology laboratory for the homologous vaccine strain, A/Hong Kong/125/2017 (H7N9) and heterologous H7N9 strains, A/Shanghai/2/2013 and A/Guangdong/17SF003/2016. Assay results are reported as a reciprocal titer with values of  $10 \times 2^k$ , where  $k=0, 1, 2$ , etc. The lower limit of detection for the HAI and Neut assays is 10, values below the lower limit of detection are imputed for analysis as one-half the limit of detection ( $10/2 = 5$ ). For analysis, the geometric mean (calculated on natural log scale) of repeated results for each sample will be computed and used as the response for all subsequent calculations. The variation arising from multiple measurements for an individual at a single time point is not used in subsequent calculations. See Section 3.3 for definitions of derived variables for the analysis of HAI and Neut data.

An addendum to the SAP will be generated to outline the planned analyses for NA antigen specific antibody responses and HA stem-specific antibody responses when assay development is complete, and results are available.

All immunogenicity data will be uploaded into the SDCC's electronic data capture system.

---

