### 8.1. Primary Immunogenicity Analysis

The primary immunogenicity endpoints of HAI and Neut seroconversion, percentage of subjects with titer  $\geq 40$ , and GMTs against the homologous A/H7N9 vaccine strain 21 days after study vaccination will be summarized as described above. Regression modeling of seroconversion and log titers is planned as described in Section 8.3.2. No formal hypothesis testing is planned.

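### SAP 8.3.2 lets an undefined normality check, made after the data are seen, decide whether the log-titer models are fitted, and makes no provision for the unequal variances that a titer floor can create

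*SAP*

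**What the plan says.** SAP 8.3.2 first commits to the models: "Logistic and multivariable linear regression will be utilized to test for the effects of prior vaccination with 2013 A/H7N9 IIV" and of adding AS03, on seroconversion and on GMT at 21 days, with similar models for HAI and Neut. It then attaches a condition to the linear model only: "If the available titer data meets the required assumptions of normality after log transformation, multiple linear regression will be fit". It goes on without condition: "Parameter estimates for the multiple linear regression models will be presented in" Tables 40 to 43. SAP 8.1, on the primary immunogenicity endpoints, adds "Regression modeling of seroconversion and log titers is planned as described in Section 8.3.2" and says that no formal hypothesis testing is planned.

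SAP 8.3.2 says modeling assumptions will be checked by standard diagnostics, with the SAS INFLUENCE option as the example. Models 2A and 2B each have one error term. No robust variance or alternative model is named.

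On the data, SAP 4.5.2 reports titers as 10×2^k, with a detection limit of 10: "values below the lower limit of detection are imputed for analysis as one-half the limit of detection", that is, 5. SAP 3.3 takes the geometric mean of two replicates. In the shells for Tables 40 and 42 the reference levels are vaccine without AS03 and the naïve stratum.

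**The concern.** The text both promises Tables 40–43 and makes them optional after the data are seen. It does not say what test or threshold applies, whether raw titers or residuals are judged, whether HAI and Neut are judged separately, or what replaces the model if the check fails.

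The condition also looks at the wrong property. A two-fold grid with a floor is never normal, so a strict reading could suppress usable models. Passing the check would say nothing about variance. A stratum with many titers at 5 has a compressed spread, and an ordinary linear model gives every arm the same pooled variance.

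A floor is plausible here. Protocol 2.1 says "Due to the poor immunogenicity of A/H5 and A/H7 vaccines, the inclusion of adjuvants was evaluated", and Protocol 2.2 says the 2013 vaccine "does not induce protective HAI or Neut antibodies against the Yangtze River Delta lineage". The naïve stratum is the likeliest to sit low, and it supplies the reference row.

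At stake are the standard errors, confidence intervals and p-values in Tables 40–43, and the covariate-adjusted estimates of Model 2B. Model 2A is saturated (ten arms, ten parameters), so its point estimates can be rebuilt from the arm GMTs. Those of Model 2B cannot.

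**Working it through.** **The plan's own figure.** Neither document gives an SD, GMT ratio or power for the log-titer models. The nearest design figure is Protocol Table 13 (SAP Table 7): 80% power for 0.10 versus 0.32 responders at 50 per arm. Exact enumeration of the likelihood ratio test gives 0.800. It concerns proportions and does not bear on what follows.

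**Inputs from the documents.** 50 per arm in the MF59, AS03 and unadjuvanted strata, 30 per arm in the mixed-prime and naïve strata, 420 in total; two replicates on the 10×2^k scale; below 10 set to 5.

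**Assumed inputs.** Between-subject log2 SD 1.6 (range 1.2 to 2.0), replicate log2 SD 0.4, latent values rounded or truncated to the grid, and the latent GMTs below. For naïve GMT 5, one replicate has SD √(1.6² + 0.4²) = 1.649. It falls below 10 with probability Φ(1/1.649) = 0.73 if truncated, or Φ(0.5/1.649) = 0.62 if rounded. Both replicates do so in about 68% and 57% of subjects.

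**Step 1: non-normality alone.** With all arms at one GMT, hence equal variance, Shapiro–Wilk rejects normality of residuals in 64–100% of simulated trials, while the ordinary model's type I error stays at 4.3–5.1%.

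**Step 2: unequal variance by hand.** In a parallel calculation (latent natural-log SD 1.2, replicate log2 SD 0.5, truncated), the observed natural-log SD is 0.60 at GMT 5, 0.84 at 10, 1.02 at 20, 1.15 at 40 and 1.21 at 80. Take GMTs of 40/80/10/20/5 for MF59/AS03/unadjuvanted/mixed/naïve, with no AS03 effect:

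- Pooled variance = (100×1.15² + 100×1.21² + 100×0.84² + 60×1.02² + 60×0.60²)/420 = 433.2/420 = 1.03, so pooled SD = 1.016.
- AS03 in naïve subjects (printed): the effective cut-off is 1.96×1.016/0.60 = 3.32, so two-sided rejection is 0.1%.
- AS03-primed × AS03 interaction (printed): true variance 1.21²×2/50 + 0.60²×2/30 = 0.0826; pooled variance 1.03×(2/50 + 2/30) = 0.110. The cut-off is 1.96×√(0.110/0.0826) = 2.26, so rejection is 2.4%.
- AS03 within the AS03-primed stratum (not printed): the cut-off is 1.96×1.016/1.21 = 1.65, so rejection is 10%.

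**Step 3: simulation of Model 2A**, 10,000 trials per setting, nominal 5%, pooled errors, over log2 SD 1.2 to 2.0:

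| Latent GMTs (MF59/AS03/unadj./mixed/naïve) | AS03 in naïve (printed) | AS03 in least-floored primed strata (not printed) |
|---|---|---|
| all 80 | 4.5–5.4% | 4.5–5.4% |
| 80/80/80/80/5 | 0–0.2% | 5.9–6.8% |
| 40/80/10/20/5 | 0–0.5% | 7.5–10.3% |
| 10/80/5/10/5 | 0.2–1.2% | 12.3–16.6% |

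At log2 SD 1.6 the interaction rows reject in 0.2–5%. HC3 gives 4.4–5.6% for the naïve AS03 and interaction rows. Coverage of 95% intervals for the priming contrasts is 95.0–99.8% pooled and 94.7–95.4% with HC3. Model 2B with its four covariates, run on the last two rows only, gives 0.1–1.1% for AS03 in naïve subjects.

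**Step 4: power.** For a 2-fold latent AS03 effect in naïve subjects (GMT 5 versus 10), power over Models 2A and 2B is 18–32% pooled and 50–56% with HC3.

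**The case against.** The strongest reply is that a reader might infer that Tables 40–43 will overstate AS03 effects in well-primed subjects. The documents do not support that. With the naïve stratum as reference, the shells print AS03 in naïve subjects, each stratum against naïve without AS03, and the interactions. AS03 within a primed stratum is the main effect plus an interaction, which neither SAP 8.3.2 nor the shells plan to report. The 6–17% inflation belongs only to that derived contrast. For the printed rows the error is conservatism and lost power. This part of the reply stands.

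It also stands that the size is wholly assumed. With no stratum near the floor, pooled errors are correct.

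Nor can one infer that the primary immunogenicity results hang on the condition. Arm GMTs with t-based intervals, the reverse cumulative curves and the logistic models are unconditional. SAP 6.8 says no specific null hypothesis is tested, and Protocol 11.6.3 calls such models exploratory.

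The diagnostics sentence could be read to cover equal variance, since its list is only an example. It still names no action if a check fails.

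Finally, HC3 can break down. If 96% of a stratum were at 5, an arm of 30 would be entirely at 5 with probability 0.96^30 = 0.29, and both arms with 0.29² ≈ 0.09. The robust error for that contrast in Model 2A would then be zero. That calls for a rule, given in the fix, not for keeping the normality condition.

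**Conclusion.** The documentary point is certain: the condition is undefined, judged after the data are seen, lacks a fallback, and conflicts with tables promised without condition. The statistical point holds under assumptions. If the naïve stratum sits near the floor and some primed strata do not, pooled errors make the printed AS03 row for naïve subjects reject almost never under the null (0–1%) and cost it roughly half of its power or more. HC3 restores close to nominal error. If few titers are below 10, the choice of standard error hardly matters.

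Robust errors correct inference on the SAP's own titer, with values below 10 set to 5. They do not undo the floor's compression of GMT ratios. A left-censored model would address that but targets a different quantity, so it is at most a sensitivity analysis.

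The change is worth making because it is specific and nearly free. The models are exploratory, so it is not a threat to the trial's main results.

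**What to change.** In SAP 8.3.2, delete the normality condition and state:

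> Models 2A and 2B will be fitted for both HAI and Neut with heteroscedasticity-robust (HC3) standard errors. Diagnostics and the share of titers below 10 in each arm will be reported but will not decide whether a model is presented. Where all titers in both arms of a contrast are at 5, that contrast will be reported descriptively only.

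If AS03 effects within primed strata are later derived from the model, they should use the same robust errors.

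Optional: add the same-strain Day 1 log titer, already collected, to Model 2B for the AS03 contrasts, and keep the priming contrasts without it because priming can affect baseline. The gain is modest, about 1–11% of interval width under the assumptions tried, and smallest when most baselines are below 10.

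Cost: SAP wording and minor programming, plus one degree of freedom if the Day 1 titer is added. No new data are needed.
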